### 1.1 Overview of Non-Clinical Studies

Exploration of GI disease in animal models of CF has focused on impaired bicarbonate and chloride secretion related to CFTR dysfunction in order to help explain the clinical manifestations of the disease. In these models the GI tract demonstrates physiological sequelae of impaired CFTR function similar to that seen in the lungs. This includes, but is not limited to, altered fluid pH(1, 3), thickened mucus secretions(2, 4), increased inflammation(5), impaired motility(5, 6) and dysbiosis(7, 8).

CFTR is present throughout the GI tract from the esophagus to the rectum(9). As the biologic and physiological processes of the intestine and its associated GI organs change, so do the manifestations of impaired CFTR activity. However, CF animal models have demonstrated that these manifestations do not exist in isolation, with CF therapies often having benefits to the GI tract beyond their primary target, the lung. As an example, successful treatment of dysbiosis and/or small intestinal bacterial overgrowth (SIBO) in mouse models results not only in quantitative and qualitative changes in bacterial flora, but also decreased mucus accumulation, decreased inflammation and improved intestinal transit times(10).

CF animal models have been effective in describing the multiple GI manifestations of CF and providing an initial understanding of the complex interactions among symptoms. However, due to differences of severity among CFTTR-related phenotypes between species, animal models have a limited role in therapeutic investigations necessitating an increased focus on clinical studies.

## 1.2 Overview of Clinical Studies

There are currently no large, multicenter prospective clinical trials examining management of many of the GI symptoms in people with CF. Current recommendations in the CF literature still are largely based on expert consensus and opinions. However, generalized GI symptoms seen often in CF include nausea, abdominal pain, abdominal distension, constipation or diarrhea, decreased appetite and weight loss and these symptoms are crucial factors that impact patient's quality of life as well as the maintenance of an optimal nutritional state in people with CF(1, 3). The majority of studies of GI comorbidities seen in CF have been investigated in small single center studies, often retrospective. For example, although constipation is common in people with CF, and a source of significant abdominal pain, available studies have focused on the less common distal intestinal obstruction syndrome (DIOS). Studies focused on the lifetime prevalence of constipation are scarce, but some report that constipation is common in pediatrics with a prevalence ranging between 26-47% and 42% in adults(2, 4). The main obstacle in formulating formal treatment recommendations for the GI symptoms in CF has been the overlap of many GI symptoms simultaneously in the same patient with CF and the lack of a focused symptom-based questionnaire that correctly identifies constipation and other GI disorders specifically in patients with CF(1, 3-5). The pathophysiology of many of these GI symptoms in CF is unique and perhaps different than what is seen in the general population with multifactorial causes which include both an increased viscosity of intestinal mucus with subsequent prolonged transit times in the stomach (gastroparesis), small intestinal bacterial overgrowth (SIBO), or colon (colonic dysmotility or fecal incontinence due to severe constipation) (5, 6). In this study, we will focus on more common GI conditions that impact the lives of a large number of people with CF.

Several validated questionnaires exist for capturing the overlap of GI symptoms in the general population and for categorizing them into specific groups based on most likely GI diagnoses. The validated questionnaires most cited and often used by the National Institutes of Health (NIH) and accepted by the FDA for purposes of clinical drug trials are the ROME IV questionnaires(11), Patient Assessment of Gastrointestinal Symptoms (PAGI-SYM)(12), Patient-Assessment of Constipation Symptoms (PAC-SYM)(13) and Patient- Assessment of Constipation Quality of Life (PAC-QOL)(14).

ROME IV is used as a diagnostic tool for what was previously termed “Functional Bowel Diseases”; however, it does not stratify patients based on symptom intensity and was purely formed for diagnostic purposes. It is a long and laborious set of questionnaires and although also validated in children more than 4 years of age, its limitations include the inability to analyze symptom severity. In contrast, the PAC-SYM is a 12-item questionnaire that evaluates many different GI symptoms including nausea, vomiting, upper or lower abdominal pain, constipation and other questions related to stool habits(13). A higher score corresponds with worse symptoms; with a range from 1 to 4 points. In the general adult population, a decrease in score of about 1 point indicates moderate improvement and a decrease of about 0.5 points indicating minimal improvement. Another validated scale system is the Bristol Stool Scale discussed above(9, 15) which is primarily based on a pictorial identification of stool consistency and validated both in the pediatric and adult population. A lower score on the Bristol Stool Scale (Type 1 and 2) corresponds with harder stool, whereas a higher score suggests diarrhea (Type 6, 7) with total range of scores ranging from 1 to 7.

The PAGI-SYM is a 20-item questionnaire with six subscales: heartburn/regurgitation, fullness/early satiety, nausea/vomiting, bloating, upper abdominal pain, and lower abdominal pain and has good internal consistency and reliability ( $\alpha=0.79-0.91$ ) (12). This questionnaire correlates well with the PAGI-QOL scores ( $p$  value  $< 0.0001$ ) and was developed in fact in conjunction with a disease-specific QOL instrument, the PAGI-QOL, making it a robust internationally utilized instrument. The PAGI-SYM is a helpful questionnaire for assessing symptom severity with good construct validity in subjects with reflux, dyspepsia, abdominal pain and gastroparesis - all symptoms and disorders which people with CF could have. The initial purpose of this questionnaire was its application in clinical trials and for assessment of effectiveness of new medical treatments.

In addition to the PAGI-QOL, other important quality of life measures also exist for constipation and would be important to capture in the CF population. The PAC-QOL has 28 questions also rated on a 5 point Likert scale from 0 to 4 which range from not at all (0) to all of the time (4) (14). These questions are focused more on the intensity of bloating and constipation, as well as covering 4 subscales including worries and concerns (11 items), physical discomfort (4 items), Psychosocial discomfort (8 items) and satisfaction of treatment (5 items).

While this project collects data needed to develop protocols for several key GI symptoms in people with CF, we have chosen constipation as the first symptom we will be addressing in our CF patient population. Clear definitions of chronic constipation in CF do not exist but are needed in establishing a diagnosis and subsequent treatment plans in the acute and chronic settings. The most commonly accepted definition of constipation has been based on ROME IV criteria defining constipation as less than 3 bowel movements a week. The FDA uses this definition in combination with endpoints such as the number of CSBM and Bristol Stool Scale Type 1 and 2 as defining constipation(16). The FDA's PROMIS also defined chronic constipation as decreased stool frequency as measured by the number of CSBM a week to assess treatment response and for the purposes of clinical trials(8). Abdominal pain and discomfort were excluded in the definition of constipation although these are common in our patients with CF(16). The European Society for Pediatric Gastroenterology, Hepatology and Nutrition (ESPGHAN) has proposed a definition of constipation in CF which considers: 1) abdominal pain and/or distention, 2) reduced frequency or increased consistency of stool in the last few weeks or months, and 3) Symptoms 1 and 2 are relieved by laxatives(17). However, this definition was primarily proposed to differentiate constipation from DIOS. It remains to be seen whether any of these definitions adequately describe the experience of constipation in a patient with CF that is relevant for clinically and/or research utility.

Most of the current recommendations for treatment of constipation in CF are based on expert practices and guidelines rather than formal clinical trials. Given the lack of clinical data, Freeman et al.(18) has come up with an algorithm for treatment of constipation in CF which is based primarily on expert opinion and which has not been formally tested yet in the clinical setting. Our proposal would use GI-symptomatology questionnaires to understand the multiple overlapping GI symptoms in people with CF. This would be followed by interventions directed at the most high-frequency symptoms.

## 2 STUDY RATIONALE

There are currently no large, multicenter prospective clinical trials examining management of constipation or other GI symptoms in people with CF. Current recommendations in the CF literature are largely based on expert consensus and opinions. Yet, constipation and other GI symptoms are crucial factors in QOL and maintenance of optimal nutritional state in people with CF. This study will use GI-symptomatology questionnaires to understand the multiple overlapping GI symptoms in people with CF. This would be followed by studies to improve GI outcomes through establishing evidence-based algorithms, starting with constipation. In the future, we would also like to evaluate the impact of CF modulators on common GI symptoms and evaluate how this might impact the development of symptom-specific algorithms.

### 2.1 Risk / Benefit Assessment

As an observational study, there is no anticipated direct benefit to subjects.

## 3 STUDY OBJECTIVES

### 3.1 Primary Objective

Assess the feasibility of electronic PROs conducted outside-the-clinic.

### 3.2 Secondary Objectives

- Estimate the prevalence and variability of GI symptoms occurring in pediatric and adult patients with CF
- Describe current management of GI symptoms in patients with CF
- Gather information to guide and inform on the design of future algorithm-based approaches to treating GI symptoms in people with CF

## 4 STUDY DESIGN

### 4.1 Study Overview

This is a prospective, multicenter, observational study designed to collect gastrointestinal related data in patients with CF.

Eligible subjects will be consented and enrolled in the study at the Enrollment Visit. At the visit, the subject or parent/guardian will complete the PROs using their mobile device (e.g., smartphone or tablet). The PROs will consist of four questionnaires: Patient Assessment of Constipation-Symptoms (PAC-SYM), Patient Assessment of Gastrointestinal-Symptoms (PAGI-SYM), Patient Assessment of Constipation Quality of Life (PAC-QOL) and the disease-specific questionnaire. The disease-specific questionnaire will include the Bristol Stool Scale and will collect information on presence of fecal incontinence, stool quality and frequency. At the Enrollment Visit, weight and height will be collected in addition to medical history and concomitant medication information. The subject or parent/guardian will complete the PROs outside-the-clinic setting per the Schedule of Events using their mobile device.

## 5 CRITERIA FOR EVALUATION

### 5.1 Primary Endpoint

Percentage of scheduled outside-the-clinic assessments with at least one of the four PROs fully completed.

### 5.2 Secondary Endpoints

#### Assess the feasibility of electronic PRO surveys conducted outside-the-clinic setting:

1. At each scheduled outside-the-clinic assessment, number (%) of subjects with at least one PRO fully completed
2. For each PRO, number (%) of subjects with fully completed questionnaires at each scheduled outside-the-clinic assessment and overall
3. Number (%) of completed PROs by subject, site, and other demographic and clinical features

#### Estimate the prevalence and variability of GI symptoms:

- Evaluate prevalence of protocol-defined constipation:
  4. Number (%) of enrolled subjects with any occurrence of constipation during 1 month of follow-up (the period prevalence)
- Evaluate frequency and severity of each GI symptom at scheduled assessments and overall:
  5. Number (%) of subjects with presence of GI symptom

6. Distribution of severity scores of GI symptom
7. Mean severity score of GI symptom
8. Distribution of stool frequency and type by Bristol Stool Scale
9. Change in distribution of GI symptoms and stool frequency/type from enrollment visit overall and by whether subjects were receiving treatment

- Evaluate PRO scores overall and by sub-scale at scheduled assessments:
  10. Mean PRO score
  11. Within and across subject variability of PRO scores
  12. Mean PRO scores (also mean differences and 95% confidence interval) comparing subjects with constipation to those without constipation
- Evaluate alternative CF specific definitions of constipation:
  13. Examine alternative definitions of constipation that are CF specific based on correlation with PRO questionnaires and maximizing the area under the receiver operating characteristic curve (ROC curve) for PAC-SYM scores
  14. Number (%) reporting constipation based on patient self-assessment. Examine concordance of self-reported constipation against protocol/alternate definitions using Cohen's kappa coefficient

#### **Describe current management of GI symptoms:**

- Evaluate treatment for GI symptoms and constipation at time of enrollment visit:
  15. Number (%) of all subjects receiving treatment
  16. Number (%) of all subjects initiating treatment
  17. Number (%) of all subjects receiving treatment by Medication class/type
  18. Among subjects with GI symptoms and constipation, number (%) receiving treatment
- Evaluate symptom scores due to treatment:
  19. Mean PRO scores (also mean differences and 95% confidence interval) comparing subjects receiving treatment for GI symptoms to those not receiving treatment
  20. Among subjects receiving treatment for constipation, mean absolute change in PRO scores over time overall and by medication type/class

## **6 SUBJECT SELECTION**

### **6.1 Study Population**

Subjects with a diagnosis of CF who meet all of the inclusion and none of the exclusion criteria will be eligible for participation in this study.

### **6.2 Inclusion Criteria**

1. All genders  $\geq$  2 years of age at time of consent
2. Documentation of a Cystic Fibrosis (CF) diagnosis as evidenced by one or more clinical features consistent with the CF phenotype and one or more of the following criteria:
  - Sweat chloride equal to or greater than 60 mEq/liter by quantitative pilocarpine iontophoresis test (QPIT)

- Two well-characterized mutations in the cystic fibrosis transmembrane conductance regulator (CFTR) gene
- Abnormal nasal potential difference (change in NPD in response to a low chloride solution and isoproterenol of less than -5 mV)

3. Enrolled in the Cystic Fibrosis Foundation Patient Registry (subjects may enroll in the Registry at Enrollment Visit if not previously enrolled)
4. Written informed consent (and assent when applicable) obtained from subject or subject's legal representative
5. Willing to complete questionnaires on mobile device
6. Able to use the Medidata Patient Cloud mobile application for completing the questionnaires

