### **9.1.9 Disease-specific questions**

The Bristol Stool Scale is a visual assessment of stool consistency. In addition, there are questions related to stool quality, frequency and presence of fecal incontinence. These will be completed as noted in the Schedule of Events. The questionnaire takes approximately 5 minutes to complete. For subjects  $\geq 2$  years of age to  $< 12$  years of age, the parent/guardian will complete these questions. For subjects  $\geq 12$  years of age, the subject will complete these questions.

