2.3 Definition of the Analysis Populations

Enrollment:

An enrolled participant was defined as a participant who had met all eligibility criteria, and fully completed (i.e. no question left unanswered) at least one of the ePRO questionnaires (PAC-SYM, PAGI-SYM, PAC-QOL, and disease-specific) at baseline.

Baseline:

Baseline refers to the enrollment visit of enrolled participants, at which informed consent was given, eligibility was met, and medical history was collected.

Follow-up weeks:

GALAXY Statistical Analysis Plan 12/16/2019 - CONFIDENTIAL

Follow-up occurred at week 1 (day 7, +1), week 2 (day 14, +1), and week 4, (day 28, +1). These were outside-of-clinic, i.e. participants are asked to complete the ePRO via their mobile devices. The questionnaires took approximately 10 minutes to complete. For participants \geq 2 years of age to $<$ 12 years of age, the parent/guardian completed the questionnaire. For participants \geq 12 years of age, the participant completed the questionnaire.

Protocol-defined constipation:

Per protocol, constipation is defined as $<$ 3 bowel movements in the past week and/or Bristol Stool type 1 or 2.

3. Overview of Planned Analyses

Unless otherwise noted, the endpoints of this study are mostly descriptive, with all continuous outcomes such as symptom severity and PRO scores evaluated using descriptive statistics such as mean, median, standard deviation, and 95% confidence intervals. Presence/absence of symptoms will be shown as percentages and corresponding 95% confidence intervals calculated using the Wilson method. Longitudinal models will be mixed-effect models with participant-specific random effect and compound symmetry covariance structure. Except where otherwise noted, all tests will be two-sided and statistical significance will be determined at the 0.05 level. No adjustment for multiple comparisons will be made.

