[1] 'All Enrolled Participants' are those who met study eligibility criteria and fully completed at least ePRO at baseline visit (Visit 1).

[2] Pancreatic Insufficient is defined as PERT use and/or fecal elastase or other diagnostic test at baseline.

Note on missing demographic data

A.3 Summary of ePRO Completion

Exhibit 3.1.x Completion of ePRO Questionnaires – [All or Subgroups Defined by Age here]

This table summarizes ePRO completion rate across baseline and follow-up weeks. “Fully completed” a questionnaire is defined as having responded to all questions with no missing responses.

Week	PAC-SYM	PAGI-SYM	PAC-QOL	Disease-Specific	Fully Completed at Least One ePRO	Fully Completed all ePROs
Baseline (N=n)	n (%)					
Week 1 (N=n)	n (%)			X		
Week 2 (N=n)	n (%)			X		
Week 4 (N=n)	n (%)					
All follow-up weeks	n (%)					

Note: PAC-QOL was only collected at Baseline and Week 4.

Exhibit 3.1.1 Completion of ePRO Questionnaires – All Participants

Exhibit 3.1.2 Completion of ePRO Questionnaires – Age <18 Years

Exhibit 3.1.3 Completion of ePRO Questionnaires – Age ≥18 Years

Exhibit 3.2.1 Missing Data for ePROs by Follow-up Week and Participant

This figure helps to visualize the number of not-fully-completed ePROs at each week by participant. Data for each study participant is represented by a row. The color indicates the number of not-fully-completed ePROs at each week. For example, at baseline, enrolled participants are defined as those with eligibility and fully completed at least one ePRO. Hence, for each participant at baseline, there can only be zero, one, two, or three ePROs missing. Similarly, since PAC-QOL is not collected at Weeks 1 and 2, there can only be zero, one, two, or three ePROs missing.

[figure not shown]

Exhibit 3.2.2 Missing Data for ePROs by Participant with Age < 18
Exhibit 3.2.3 Missing Data for ePROs by Participant with Age ≥ 18

Exhibit 3.3 Completion of ePROs by Site

This table summarizes ePRO completion by site

Site	Number of Participants	Fully Completed at Least One ePRO at All Follow-Up Weeks (Weeks 1,2 & 4)	Fully Completed all ePROs at All Follow-Up Weeks (Weeks 1, 2 & 4)
Site 1			
Site 2			
...			
Site s			
Overall			

A.4 Summary of PAC-SYM, PAGI-SYM, and PAC-QOL Scores

Exhibit 4.1 Distributions of Total Scores for PAC-SYM, PAGI-SYM, and PAC-QOL for All Participants

This figure summarizes the total scores for PAC-SYM, PAGI-SYM, and PAC-QOL at each week and overall, for all participants.

[figure not shown]

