Stool Symptoms (NN=nn)									
PAGI-SYM Total Score (NN=nn)									
Nausea/Vomiting (NN=nn)									
Post-Prandial Fullness/Early Satiety (NN=nn)									
Bloating (NN=nn)									
Upper Abdominal Pain (NN=nn)									
Lower Abdominal Pain (NN=nn)									
Heartburn/Regurgitation (NN=nn)									
PAC-QOL Total Score (NN=nn)									
Physical Discomfort (NN=nn)									
Psychosocial Discomfort (NN=nn)									
Worries and Concerns (NN=nn)									
Satisfaction (NN=nn)									

A.5 Summary of Prevalence and Variability of GI Symptoms

Exhibit 5.1.1 Summary of Disease-Specific Questionnaire – All Participants

This table summarizes the GI disease-specific questionnaire for all participants. All questions were based on patient's experience in the last week.

		Baseline (N=n)	Week 1 (N=n)	Week 2 (N=n)	Week 4 (N=n)
Bowel Movements	<3 Bowel Movements ≥3 Bowel Movements		n (%)		
Self-Described Bowel Pattern:	Normal Constipated Diarrhea Alternating Constipation and Diarrhea				
Bristol Stool Scale ^[1] :	1 (Hard Lumps) – 2 3 – 5 6 – 7 (Watery) Missing				
Leakage of Stool:	Yes				
Protocol-Defined Constipation ^[2]:	Yes				

[1] Question for Bristol Stool Scale: describe what your stool looked like on most days in the last week when you had a bowel movement?

[2] Protocol-defined constipation is defined as less than 3 bowel movements and/or Bristol Stool type 1 or 2 in the past week

Exhibit 5.1.2 Summary of Disease-Specific Questionnaire – Age < 18

Exhibit 5.1.3 Summary of Disease-Specific Questionnaire – Age ≥ 18

Exhibit 5.2.1 Demographics and Baseline Characteristics by Protocol-Defined Constipation at Baseline.

This table summarizes demographics and baseline characteristics, stratified by protocol-defined constipation at Baseline Visit.

	Protocol-Defined Constipation at Baseline		All Enrolled Participants (N=n)	Fully Completed at Least One ePRO at all Follow-up Weeks (N=n)	CF Registry (N=n)
	Yes (N=n)	No (N=n)			
Sex at Birth, n (%)	Female				
	Male				
Age Distribution, n (%)	<6 years				
	≥6 – 12 years				
	≥12 – 18 years				
	≥18 – 24 years				
	≥24 – 30 years				
	≥30 years				
	Mean (SD)				
	Median				
	Min, Max				
Race, n (%)	White				
	American Indian or Alaska Native				
	Black or African American				
	More than One Race				
	Unknown or Not Reported				
Ethnicity, n (%)	Hispanic or Latino				
	Not Hispanic or Latino				

CF Therapeutics Development Network Coordinating Center
GALAXY-OB-18

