Exhibit 6.2.x Evaluation of Concordance between Self-Defined Constipation and Constipation Defined by [Protocol or Specific Rules]

This table shows the concordance between self-defined constipation and the definition of interest

	Self-Defined Constipation		Cohen's Kappa
	Yes	No	
Constipation Definition of Interest:	Baseline (N=n)	Yes No	n (%)
	Week 1 (N=n)	Yes No	
	Week 2 (N=n)	Yes No	
	Week 4 (N=n)	Yes No	
	Overall (NN=nn)	Yes No	
			x

Exhibit 6.3.1 Evaluation of Protocol-Defined Constipation at Baseline and Constipation Treatment.

This table shows the relationship between constipation at baseline and constipation treatment. Constipation is defined per protocol.

		Constipation at Baseline (N=n)		No Constipation at Baseline (N=n)		All Participants at Baseline (N=n)	
		On Treatment (N=n)	Not on Treatment (N=n)	On Treatment (N=n)	Not on Treatment (N=n)	On Treatment (N=n)	Not on Treatment (N=n)
Week 1	Constipation	n (%)	n (%)				
	No Constipation	n (%)	n (%)				
	Unknown [1]	n (%)	n (%)				
Week 2	Constipation						
	No Constipation						
	Unknown [1]						
Week 4	Constipation						
	No Constipation						
	Unknown [1]						
All Follow-up Weeks [2]	Constipation						
	No Constipation						
	Unknown						

[1] Unknown status of constipation at each week is defined as incomplete Disease-Specific Questionnaire

[2] To summarize all follow-up weeks, constipation status implies that a participant had at least one or more week where they met the protocol definition of constipation.

Exhibit 6.3.2 Evaluation of Self-Defined Constipation at Baseline and Constipation Treatment.

This table shows the relationship between self-defined constipation at baseline and constipation treatment. Constipation is defined as choosing "Constipated" or "Alternating constipation and diarrhea" as answer for question 2 ("How would you describe your bowel pattern in the last week? (Select one)") on the Disease-Specific Questionnaire.

		Constipation at Baseline (N=n)		No Constipation at Baseline (N=n)		All Participants (N=n)	
		On Treatment (N=n)	Not on Treatment (N=n)	On Treatment (N=n)	Not on Treatment (N=n)	On Treatment (N=n)	Not on Treatment (N=n)
Week 1	Constipation	n (%)	n (%)				
	No Constipation	n (%)	n (%)				
	Unknown [1]	n (%)	n (%)				
Week 2	Constipation						
	No Constipation						
	Unknown [1]						
Week 4	Constipation						
	No Constipation						
	Unknown [1]						
All Follow-up Weeks [2]	Constipation						
	No Constipation						
	Unknown						

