Appendix C: Pre-Specified GI Symptoms of Interest

PAC-SYM:

- Incomplete BMs (Q8)
- Straining or squeezing to try to pass a BM (Q11)
- Feeling you have to have a BM but cannot pass it (Q12)

PAGI-SYM:

- Regurgitation or reflux (fluid or liquid coming up) (Q18)
- Nausea (Q1)
- Vomiting (Q3)
- Upper abdominal pain (Q10)
- Loss of appetite (Q7)
- Stomach fullness (Q4)
- Bloating (Q8)
- Stomach for belly visibly larger (Q9)

Disease-specific questionnaire:

- Fecal incontinence

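### The plan has no rule for the stool-leakage item in children not yet toilet-trained, which distorts the under-18 incontinence figure and can discard usable constipation data

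*Protocol*

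**What the plan says.** Protocol 6.2, criterion 1, sets the lower age limit at "2 years of age at time of consent". No inclusion or exclusion criterion mentions toilet training. Exclusion 1 concerns a condition or abnormality in the investigator's opinion, which does not clearly describe a normal two-year-old.

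Protocol 9.1.9 says of the disease-specific questionnaire that "there are questions related to stool quality, frequency and presence of fecal incontinence". For ages 2 to under 12, the "parent/guardian will complete these questions".

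SAP Appendix C lists "Fecal incontinence" as a pre-specified symptom with no age limit. Exhibits 5.1.1 to 5.1.3 have a "Leakage of Stool" row that shows only the positive count, for everyone, for under 18 and for 18 and over. There is no not-applicable row.

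SAP 2.3 takes a questionnaire as "fully completed (i.e. no question left unanswered", and Exhibit 3.1 repeats this as "having responded to all questions with no missing responses". Exhibit 5.2.2 keeps only participants who meet that standard for the disease-specific questionnaire at baseline and every follow-up week. Exhibit 5.2.3 requires it at least once, and Exhibits 6.4 and 6.5 at least once during follow-up. Footnote 1 of Exhibit 6.3.1 reads: "Unknown status of constipation at each week is defined as incomplete Disease-Specific Questionnaire".

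Protocol-defined constipation (Protocol 15.4, SAP 2.3) uses only two inputs: stool frequency and Bristol type.

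**The concern.** Protocol 1.2 presents fecal incontinence as a consequence of severe constipation and criticizes an earlier CF survey for not measuring it. This study is therefore expected to supply the figure. In the pediatric column that figure would mix disease with ordinary diaper use, in a proportion set by how each parent reads an item that does not apply to the child.

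The second consequence concerns constipation. Period prevalence is the endpoint on which the sample size rests, and it needs only stool frequency and Bristol type. Its two tables nevertheless require the whole questionnaire to be complete, so a skipped leakage item can remove a child whose constipation status is known. The children lost in this way would be the youngest ones, not a random subset.

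**Working it through.** **1. The three possible answers for a child not yet toilet-trained**

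| Parent's answer | Leakage row, under 18 | Disease-specific questionnaire | Constipation tables |
|---|---|---|---|
| Yes | counted as symptomatic | complete | unaffected |
| No | counted as symptom-free | complete | unaffected |
| Blank | not counted as positive | not fully completed | see step 2 |

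**2. What a blank does, exhibit by exhibit**
- Exhibit 5.2.2: one blank at any of the four assessments drops the child.
- Exhibit 5.2.3: the child is lost only if the item is blank at all four.
- Exhibits 6.4 and 6.5: the child is lost if the item is blank at all three follow-ups.
- Exhibit 6.3.1: on one reading of footnote 1, that week becomes Unknown.

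Each of these can happen with stool frequency and Bristol type both answered.

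**3. The plan's own sample size (Protocol 15.7)**
Inputs: prevalence 25%, half-width 4.5%, 12% missing.
- n = 1.96² × 0.25 × 0.75 / 0.045² = 355.7, so 356.
- Allowing for missing data: 356 / 0.88 gives 405; 356 × 1.12 gives 399. Both agree with the stated figure of approximately 400.
- With 400 × 0.88 = 352 evaluable, the half-width is 1.96 × √(0.1875 / 352) = 4.52% (Wilson: 4.51%).

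**4. Number of children affected (assumption)**
The documents give 160 pediatric participants but no age distribution below 18 and no toilet-training data. Assume an even spread over ages 2 to 17: 160 / 16 = 10 per year of age, so 20 aged 2 or 3. If 25% to 75% of these are not toilet-trained, k = 5 to 15.

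**5. Effect on the under-18 leakage figure**
Upper bound if every such parent answers yes: k / 160, that is 5/160 = 3.1 points to 15/160 = 9.4 points.

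Illustration with an assumed true rate of 5% in the other children:
- All yes: (0.05 × 155 + 5) / 160 = 8.0%; (0.05 × 145 + 15) / 160 = 13.9%.
- All no: 0.05 × 155 / 160 = 4.8%; 0.05 × 145 / 160 = 4.5%.
- All blank, with those children left out of the denominator: the rate stays at 5%, but the under-18 completion rate for the disease-specific questionnaire falls by 3.1 to 9.4 points.

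**6. Effect on constipation precision**
Removing k from the 352 evaluable gives half-widths of 1.96 × √(0.1875 / 347) = 4.56% to 1.96 × √(0.1875 / 337) = 4.62%. If all 20 children aged 2 or 3 were lost, it would be 4.66%, a widening of 0.14 points.

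**The case against.** A reader might infer that every child not yet toilet-trained must be counted either as symptomatic or as having an incomplete questionnaire. The documents do not support that. A parent can answer no, which leaves the form complete and slightly lowers the rate. The wording and response options of the leakage item are not reproduced, so a not-applicable choice cannot be ruled out. If one exists, the SAP still does not say how to count it.

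The link from a blank item to Unknown status is also open to argument. The matching footnote to Exhibit 6.3.2 adds failure to answer question 2 as a separate reason, which would be redundant if any blank made the form incomplete. Exhibit 5.1.1 carries a Missing row for Bristol type, which suggests item-level handling. That objection stands for Exhibit 6.3.1. It does not reach Exhibits 5.2.2, 5.2.3, 6.4 and 6.5, which use the defined term for full completion.

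A reader might also infer that the primary endpoint is at risk. It is largely protected, because one fully completed questionnaire is enough and PAC-SYM or PAGI-SYM can supply it. Nor does the point extend to Exhibit 5.3.1, which draws on the other three questionnaires only. Exhibit 5.2.3 recovers any child whose parent answered all items at least once.

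Finally, the affected number is assumed, and each bound takes all parents to answer alike. That is correct, and the sizes above are limits, not estimates.

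**Conclusion.** The gap is real and modest. Nothing in either document says how to score the leakage item, or set it aside, in children who are not yet toilet-trained. The younger age splits in SAP A.8 (under 6, under 12) are optional and do not isolate these children. Following the plan as written can bias the pediatric incontinence figure in either direction and can discard constipation data that are in hand.

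The size rests on the assumption of 5 to 15 affected children among 160: at most about 3 to 9 points on the under-18 leakage figure if all parents answer yes, and a much smaller understatement if all answer no. Overall constipation precision changes by at most about 0.14 points of half-width even with 20 children lost, so selective loss of the youngest matters more than loss of precision. The sample size of 400 is not in question.

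**What to change.** Two changes, both in the SAP:

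1. In Exhibits 5.1.1 to 5.1.3, and in any Exhibit 7.2 symptom row or any-symptom row that includes it, report fecal incontinence with the youngest children shown separately and excluded from the headline under-18 figure. Ages 2 to 3 would be one possible band. The sponsor should set the cutoff, using the date of birth already collected under Protocol 9.1.2. If toilet-training status was recorded, restrict to toilet-trained children instead. The SAP describes enrollment in the past tense, so a new enrollment field may come too late and should not be relied on.

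2. For all participants, derive weekly and period constipation status from the stool-frequency and Bristol items whenever these determine it. Either item alone can establish constipation; both are needed to rule it out for a week. Do not require the rest of the questionnaire. Leave the definition of full completion unchanged for the feasibility endpoints, since a rule that varied with age would muddy the study's primary objective.

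The cost is a slightly smaller pediatric denominator for one symptom, and a constipation denominator that no longer matches the completion denominator and needs a footnote.
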